#### 9.4 Data Sources

As this is a non-interventional study, only data on clinical routine practice will be documented. To facilitate accurate recording of data, patients can optionally fill in a memory aid (patient diary) to note important details.

For this disease registry, safety reporting for drugs will be covered outside the scope of this study through the local processes of spontaneous reporting.

Scheduled assessments for the study are presented in the Data Collection Flow Chart provided below (Table 1). All data elements will be collected from information routinely recorded in the

patient files/medical records. No visits or examinations, laboratory tests or procedures are mandated as part of this study.

The EQ-5D-5Land PAM-13 questionnaires need to be filled out by the patients at the physician's office.

The completed forms will be collected at the site and sent on a regular basis to the responsible CRO for data transfer. The relevant information out of the PRO questionnaire and the assessment will be manually entered into the eCRF.

**Table 1: Data Collection Flow Chart**

Variable	Baseline	Follow-up
Eligibility criteria	x	
Baseline Characteristics	x	
Vital signs	x	x
Medical History	x	
Hypercholesterolemia risk factors and predisposing comorbidities	x	x
Use pattern of previous/current lipid modifying treatment	x	x
Previous and current dietary restrictions	x	x
Concomitant medications for cardiovascular disease	x	x
Concomitant diseases For diabetic patients: Disease type and date of diagnosis, detailed treatment information, microvascular complications	x	x
Laboratory examinations (as available in medical records*) *physicians will not be required to perform any mandatory laboratory assessment for this study	x	x
Clinical events and hospitalizations		x
Management of hypercholesterolemia and physician contacts	x	x
PRO	x	x
Resource consumption/Health care utilization	x	x
ADRs related to bemedoic acid and/or bemedoic acid fixed-dose combination with ezetimibe**		x

\*\* Only applicable for Patients with bemedoic acid and/or bemedoic acid fixed dose combination with ezetimibe treatment:

## 9.5 Sample Size Calculation

As this registry is intended to collect data under real-life conditions and the statistical analysis will be performed in a purely explorative way, no primary parameter has been defined for the sample size calculation. On a pragmatic basis, data of approximately 8000 patients will be collected, whose data is to be documented both retrospectively and prospectively (over a period of 1 year). This sample size of 8000 patients will provide sufficient precision (measured by width of 95% confidence interval) for the rates of CV death, nonfatal MTI, nonfatal stroke, and coronary revascularization during one year follow up.

Assuming an absolute reduction of LDL-C across all treatment modalities in a real-life setting of 0.9 mmol/L, the sample size shall provide information for an expected change in the relative risk of major vascular events with an absolute precision of  $\pm 13\%$  (relative precision  $\pm 16\%$ ).

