	
 
○ Reduced kidney function
 
○ Drug-drug interaction
 
○ Noncompliance
 
○ Neurocognitive impairment
 
○ Other
 
○ Laboratory parameters
 
○ Lipid variables           
 
○ LDL-C
 
○ HDL-C, non-HDL-C, TC, apoB, TG, Lp(a)
 
 
 
○ Diabetes-related parameters           
 
○ fasting glucose
 
○ HbA1c
 
 
 
○ Inflammatory status           
 
○ hsCRP
 
 
 
○ Renal function parameters (GFR, serum creatinine, blood urea nitrogen (BUN))
 
○ Other laboratory parameters (liver function, serum chemistry, hematology)
 
○ HEOR parameters           
 
○ Hospital admissions
 
○ Length of hospital stay
 
○ Number of days in ICU
 
○ Interventions
 
○ Other HEOR parameters (e.g. insurance status, employment status, education)
 
○ Adherence to former and current treatment
 
○ Patient reported outcomes (EQ-5D-5L, PAM-13)
 
 
 

Data Sources	
As this is a non-interventional study, only data on routine clinical practice will be documented. To facilitate accurate recording of data, patients can optionally fill in a memory aid (patient diary to note important details).

Study Size	
Sample size considerations:
 
As this registry is intended to collect data under real-life conditions and the statistical analysis will be performed in a purely explorative way, no primary parameter has been defined for the sample size calculation. On a pragmatic basis, data of approximately 8000 patients will be collected, whose data is to be documented both retrospectively and prospectively (over a period of 1 year). This sample size of 8000 patients will provide sufficient precision (measured by width of 95% confidence interval) for the rates of CV death, nonfatal MI, nonfatal stroke, and coronary revascularization during one year follow-up. Assuming an absolute reduction of LDL-C across all treatment modalities in a real-life setting of 0.9 mmol/L, the sample size shall provide information for an expected change in the relative risk of major vascular events with an absolute precision of <math>\pm 13\%</math> (relative precision <math>\pm 16\%</math>).

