### **Eligibility Criteria**

Very High Risk and High Risk dyslipidemic patients requiring LMT's are eligible for enrolment. Further inclusion criteria

- $\geq 18$  years of age
- not simultaneously participating in any interventional study
- providing written informed consent for participation in the study (ICF)
- life expectancy  $> 1$  year

Patients will be stratified for High and Very High Risk as well as for previously and newly treated patients.

As this is a non-interventional study, no explicit exclusion criteria are defined.

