### **Patient Groups**

There are no formal patient groups planned. No comparator groups will be introduced.

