### 9.3 Variables

#### Parameters recorded during the observation period:

*To be documented at baseline (if available):*

- Eligibility
- Demographic and sociodemographic variables
- Vital signs
- Medical history, including CVD risk status-related medical history:
  - CV risk assessment with or without utilization of risk score
  - history/diagnosis and current status of dyslipidemia
  - heterozygous familial hypercholesterolemia (HeFH)
  - documented ASCVD either clinical or unequivocal on imaging
- Concomitant diseases
- For diabetic patients
  - disease type and date of diagnosis
  - treatment
  - microvascular complications
- Current concomitant medication for CVD
- Previous / current dietary restrictions
- Previous / current use of lipid-modifying treatment
 

Previous / current use of lipid-modifying treatment including details of dose, dose modification, switching, combination therapy, drug intolerance, insufficient responsiveness, investigators and patients assessment on compliance

  - Statin(s)
  - Bile acid sequestrant(s)
  - Cholesterol absorption inhibitor (Ezetimibe)
  - PCSK9 inhibitor(s)
  - Nicotinic acid
  - Drug combinations
  - Bempedoic acid and/or bempedoic acid fixed dose combination with ezetimibe
  - Other
- Laboratory parameters
  - Lipid variables
    - LDL-C
    - HDL-C, non-HDL-C, TC, apoB, TG, Lp(a)
  - Diabetes-related parameters
    - fasting glucose
    - HbA1c
  - Inflammatory status
    - hsCRP
  - Renal function parameters (GFR, serum creatinine, blood urea nitrogen (BUN))
  - Other laboratory parameters (liver function, serum chemistry, hematology)
- HEOR parameters
  - Hospital admissions
  - Length of hospital stay
  - Number of days in ICU
  - Interventions
  - Other HEOR parameters

- Adherence to former and current treatment
- Patient reported outcomes (EQ-5D-5L, PAM-13)

*To be documented at 1-year follow-up (if available):*

- Vital signs
- CVD risk status:
  - CV risk assessment with or without utilization of risk score
  - history/diagnosis and current status of dyslipidemia
  - heterozygous familial hypercholesterolemia (HeFH)
  - documented ASCVD either clinical or unequivocal on imaging
- Concomitant diseases
- For diabetic patients
  - disease type and date of diagnosis
  - treatment
  - microvascular complications
- Current concomitant medication for CVD
- Previous / current dietary restrictions
- Previous / current use of lipid-modifying treatment
 

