Numerical data will be summarised by means of standard statistics (i.e. number of available data, number of missing data, mean, standard deviation, minimum, median, maximum, lower and upper quartile). In addition, adequate graphs (e.g. bar charts, box-whisker plots) may be presented to summarize the results for some parameters. Analysis of changes in numerical parameters (as the differences in Score risk between baseline and 1-year follow up) will be done by paired Wilcoxon signed rank test and paired t-test if assumptions of parametric tests will be met. Comparison of these 1-year changes between subgroups will be done by Kruskal-Wallis test and ANOVA test if assumptions of parametric tests will be met. Also adjusted analyses for age, sex and country effects will be done. Time-to-event variables will be analyzed via a Cox proportional hazard regression model presenting hazard ratios and the corresponding 95% confidence intervals. Additionally, adjusted Cox model for age, sex and country effects will be presented. In addition, Kaplan-Meier curves will be presented for time-to-event variables. Two-sided 95% confidence intervals will be presented for important parameters, but should be interpreted in an exploratory descriptive way.

Depending on the variable(s) of interest, additional selection criteria for patients (e.g. subgroup analyses) considered in specific analyses may be used, if considered useful during the statistical

analysis. Details on the selection criteria used will be given in the Statistical Analysis Plan (SAP) and in the statistical section of the report.

The statistical analysis will be performed using SAS version 9.4 or higher

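### Does the ±13% (±16% relative) precision in Section 9.5 require a change because the plan names no contrast or reference rate for it?

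*Combined protocol and SAP*

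**What the plan says.** Section 9.5 says that no primary parameter was defined for sizing and that about 8000 patients were chosen pragmatically. It calls the precision for the one-year rates of CV death, nonfatal MI, nonfatal stroke and coronary revascularization sufficient, without a number. Then, assuming an LDL-C reduction of 0.9 mmol/L over all treatment modalities, it states that "the sample size shall provide information for an expected change in the relative risk of major vascular events with an absolute precision of" ±13%, with ±16% as the relative counterpart. The Study Size row of the Summary (Section 4) repeats this: "for an expected change in the relative risk of major vascular events with an absolute precision of" the same figures.

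Other places bear on what the relative risk could mean:

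- Patient Groups (Section 9.2.3): "There are no formal patient groups planned. No comparator groups will be introduced".
- Eligibility Criteria (Section 9.2.2): "Patients will be stratified for High and Very High Risk as well as for previously and newly treated patients". No stratum sizes are given.
- Section 9.7: "Time-to-event variables will be analyzed via a Cox proportional hazard regression model presenting hazard ratios and the corresponding 95% confidence intervals". Age, sex and country are named as adjustment variables; the factor whose hazard ratio is estimated is not named.
- Table 1 marks "Clinical events and hospitalizations" at follow-up only, but "Resource consumption/Health care utilization" at both time points. Section 9.3 lists "Hospital admissions" among the baseline items.
- Section 9.7 also states that there is no primary endpoint and that all analyses are exploratory and descriptive, with details left to the SAP.

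**The concern.** A relative risk needs a numerator rate and a denominator rate. The plan describes one cohort, rules out comparator groups, and gives no external rate, expected relative risk or group sizes. The strata could supply an internal contrast, but the sentence does not refer to them. A before/after contrast is at best hinted at. The plan speaks of retrospective as well as prospective documentation, but clinical events are scheduled for collection at follow-up only, and CV death cannot precede enrolment. The term major vascular events is not tied explicitly to the four components listed just before it.

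This is also the only numerical precision in the section. A reader might take it as evidence that the registry can estimate a treatment effect on events to within ±16%, and has no means of checking that. If the intended contrast were an internal split with few events, the true precision would be considerably worse.

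**Working it through.** **Inputs from the plan.** N about 8000; ±13% absolute and ±16% relative; 95% confidence level (stated for the event rates, taken to apply here too). **Assumed, because the plan gives none:** all event rates, all group sizes and any loss to follow-up.

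**Step 1: internal consistency.** Absolute precision divided by relative precision gives the relative risk: 0.13/0.16 = 0.8125. With rounding, the range is 0.125/0.165 = 0.76 to 0.135/0.155 = 0.87. The two figures agree, and the direction fits an LDL-C reduction. The plan does not show how 0.9 mmol/L converts to a relative risk, so the ±16% itself cannot be reproduced forward.

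**Step 2: reference rate needed for ±16% relative.** Set 1.96 × SE(log RR) = 0.16, so SE² = (0.16/1.96)² = 0.00666.

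- Whole cohort against an external rate p treated as known, with observed rate q = 0.8125p: SE² = (1 − q)/(nq). For n = 8000, q = 1.84% and p = 1.84/0.8125 = 2.27% (147 events). For n = 6400 (an assumed 20% without follow-up), q = 2.29% and p = 2.82%.
- Two groups: SE² = (1 − p)/(n₁p) + (1 − 0.8125p)/(n₂ × 0.8125p). For 8000 vs 8000, p = 4.03%. For 4000 vs 4000, p = 7.78%. For 800 reference vs 7200, p = 17.6%.

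**Step 3: forward calculation at assumed reference rates** (log-scale half-widths).

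| Contrast | 2% | 3% | 4% |
|---|---|---|---|
| 8000 vs fixed external rate | ±17.0% | ±13.9% | ±12.0% |
| 6400 vs fixed external rate | ±19.1% | ±15.5% | ±13.4% |
| 4000 vs 4000 | ±32.4% | ±26.4% | ±22.7% |

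For example, with 8000 at 2%, q = 1.625%: 1.96 × √(0.98375/(8000 × 0.01625)) = 1.96 × 0.0870 = 0.170. Multiplied by 0.8125 this is ±13.9% absolute, against the stated ±13%. The 95% interval is 0.69 to 0.96. For the equal split at 2% it is 0.59 to 1.12.

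**Step 4: which row fits the sentence.** The only stated input is an LDL-C reduction over all treatment modalities, which describes the cohort as a whole. That points to the first two rows and away from an internal split, whose sizes appear nowhere. On this reading the stated figure is about right at reference rates near 2.3% (or 2.8% with 20% loss) and conservative above that. At 1% it would be optimistic: ±24.2% with 8000.

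**Step 5: what depends on the figure.** N was not derived from it. No test, endpoint or decision rule uses it. Section 9.7 provides for two-sided 95% confidence intervals for important parameters, so event estimates reported with an interval will show the precision actually achieved.

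**The case for a change.** The strongest case for a change is that the sponsor chose to publish a number, and exploratory status does not make an uncheckable number checkable. The reference rate that would justify ±16% runs from about 2.3% to 17.6% over the contrasts above, nearly an eightfold spread (17.6/2.27 = 7.8). Section 9.5 does not defer this figure to the SAP; it presents it as a result. Single-cohort event rates, which the design can plainly deliver, get no number, although it is easily computed: 1.96 × √(p(1 − p)/8000) gives ±0.22, ±0.31, ±0.37 and ±0.48 percentage points at assumed rates of 1%, 2%, 3% and 5%. Rewording two paragraphs would cost little.

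What stands is that the basis of the figure is undocumented, and a sentence giving the reference rate, its source and the event definition would help a reader. What does not stand is that this amounts to a defect in the plan. The wide spread comes mostly from internal splits that the sentence does not suggest. The unnamed Cox factor is a detail that Section 9.7 leaves to the SAP, so it is weak evidence about sample size. The before/after reading cannot be dismissed outright: the Study population text in Section 9.2 describes chart collection back to diagnosis, though it is unclear whether that covers events. Replacing the sentence would bring in event rates and a loss to follow-up that are no better grounded in the documents than the figure they replace.

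**Conclusion.** The figure cannot be verified from the plan, but it is internally consistent and not shown to be wrong. On the whole-cohort reading that the wording favours, 8000 patients give about ±17% to ±12% relative at assumed reference rates of 2% to 4%, against ±16% stated; with an assumed 20% loss the range is ±19% to ±13%. These results assume a relative risk of 0.8125, an external rate known without error, and no allowance for clustering within sites. At a rate nearer 1% the stated precision would be optimistic.

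None of this affects the study. The sample size is pragmatic, there is no primary endpoint and the analyses are exploratory, so the same patients are enrolled and the same estimates reported whichever contrast was in mind. This is missing detail behind an illustration, and supplying it would not alter enrolment, analysis or conclusions. No change is required.

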## 9.6 Data Management

The CRO's EDC system will be used for data capture. Data will be collected in standardized English eCRFs.

A data management plan will be created in the study start phase and will describe all functions, processes, and specifications for data collection, cleaning and validation. The eCRFs will include automated plausibility checks (e.g. range checks, conditional checks, etc.) at data entry to obtain immediate feedback if data are missing, out of range, illogical or potentially erroneous and allow for correction or confirmation by the site. Concurrent manual data review will be performed based on parameters defined in the data management plan. If necessary, queries will be manually generated within the EDC system and followed up for resolution.

Critical data variables will be defined that need to be filled in by the site to be able to complete and sign the eCRF module.

Data from the project specific EDC database will be exported into SAS data sets (as per CDISC SDTM definition) for further validation and analysis.

## Data Entry/Electronic Data Capture

All data will be collected and entered directly into the CRO EDC system. Each participating site will have access to its enrolled patient data only. All sites will be fully trained on using the on-line data capture system, and on the eCRF completion guidelines and other help files. Sites will be responsible for entering patient data into the secure internet-based EDC database via the eCRF. Investigators and site personnel will be able to access their account with a unique personalized username and password. All eCRFs should be completed by designated, trained personnel as appropriate. Each eCRF is to be reviewed, electronically signed, and dated by the investigator. All changes or corrections to eCRFs will be documented in an audit trail and an adequate explanation is required.

## Source Documents

In most cases, the source documents are contained in the patients' medical record and data collected on the eCRFs must be traceable to these source documents in the patients' medical records. In some cases, the eCRF, or part of the eCRF, may also serve as source documents. In these cases, a document should be available at the investigator's site and clearly identify those data that will be recorded directly in the eCRF, and for which the eCRF will be regarded as the source document. All original source documentation is expected to be stored at the site for the longest possible time required by local applicable regulations. The site will be instructed to notify the sponsor before any destruction of medical records of study participants.

## File Retention and Archiving

To enable evaluations and/or audits from regulatory authorities or the sponsor, the investigator agrees to keep records, including the identity of all participating patients, all original signed informed consent forms and source documents. The records should be retained by the investigator according to local regulations, or as specified in the study contract, whichever is longer.

Each site will receive a study site file at study initiation which contains all documents necessary for the conduct of the study and is updated throughout the study. This file must be available for review in the event the site is selected for monitoring, audits, or inspections and must be safely archived for at least 10 years or according to local legislation respectively after completing the participation in the study. Documents to be archived include the patient screening log, copy of eCRF burned on a CD and the signed informed consent forms (ICF).

## 9.7 Data Analysis

This section describes the most relevant parts of the statistical analyses planned for a NIS/registry. All statistical methodology will be described in detail in the Statistical Analysis Plan (SAP) which will be finalized at the latest prior to database lock. All variables collected in the CRFs and/or other recordings (if applicable) and all derived parameters will be used in the statistical analysis.

A report including descriptive statistics of all documented parameters will be generated also if required for each participating country. Details on the selection criteria used will be given in the SAP and in the statistical section of the report.

Referring to the primary objective, the statistical analysis will be performed in a purely explorative descriptive way according to DSE SOP R-440.

Data will be collected at the following data collection points

- baseline ,
- 1-year prospective follow-up

Following analysis sets will be used for analysis

- The All-Documented Patient Set (APS) consists of all patients with any eCRF documentation.
- The Baseline Analysis Set (BAS) consists of all eligible patients of the APS who provide adequate baseline information.
- The Full Analysis Set (FAS) consists of all patients from the BAS with available 1-year follow-up data.
- The Safety Set (SAF) includes all patients who received at least one dose of bempedoic acid and/or bempedoic acid fixed dose combination according to their documentation in the eCRF.

No primary endpoint was defined in this study. No formal statistical tests will be performed within the statistical analysis.

All statistical analyses will be performed in a purely exploratory descriptive way.

Binary, categorical, and ordinal parameters will be summarized by means of absolute and percentage numbers within the various categories (including 'missing data' as valid category at baseline).

Numerical data will be summarised by means of standard statistics (i.e. number of available data, number of missing data, mean, standard deviation, minimum, median, maximum, lower and upper quartile). In addition, adequate graphs (e.g. bar charts, box-whisker plots) may be presented to summarize the results for some parameters. Analysis of changes in numerical parameters (as the differences in Score risk between baseline and 1-year follow up) will be done by paired Wilcoxon signed rank test and paired t-test if assumptions of parametric tests will be met. Comparison of these 1-year changes between subgroups will be done by Kruskal-Wallis test and ANOVA test if assumptions of parametric tests will be met. Also adjusted analyses for age, sex and country effects will be done. Time-to-event variables will be analyzed via a Cox proportional hazard regression model presenting hazard ratios and the corresponding 95% confidence intervals. Additionally, adjusted Cox model for age, sex and country effects will be presented. In addition, Kaplan-Meier curves will be presented for time-to-event variables. Two-sided 95% confidence intervals will be presented for important parameters, but should be interpreted in an exploratory descriptive way.

Depending on the variable(s) of interest, additional selection criteria for patients (e.g. subgroup analyses) considered in specific analyses may be used, if considered useful during the statistical

analysis. Details on the selection criteria used will be given in the Statistical Analysis Plan (SAP) and in the statistical section of the report.

The statistical analysis will be performed using SAS version 9.4 or higher

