Data Analysis	
Three populations will be defined: (1) The All-Documented Patient Set (APS) consists of all patients with any eCRF documentation. (2) patients with adequately completed recruitment information (Baseline Analysis Set / BAS population); (3) patients having

	
completed 1-year follow-up (Full Analysis Set / FAS population). (4) The Safety Set (SAF) includes all patients who received at least one dose of bemedoic acid and/or bemedoic acid fixed dose combination according to their documentation in the eCRF. For BAS, FAS and SAF binary, categorical, and ordinal parameters will be summarized by means of absolute and percentage numbers within the various categories (including 'missing data' and 'not performed in the center' as valid category at baseline). Numerical data will be summarized by means of standard statistics (i.e. number of available data, number of missing data, mean, standard deviation, minimum, median, maximum, lower and upper quartile).
 
At the final analysis the differences in the CV risk score for Very High Risk and for High Risk patients will be calculated.
 
In addition, adequate graphs (e.g. bar charts, box-whisker plots) may be presented to summarize the results for some parameters.
 
Analysis of changes in numerical parameters (as the differences in Score risk between baseline and 1-year follow up) will be done by paired Wilcoxon signed rank test and paired t-test if assumptions of parametric tests will be met. Comparison of these 1-year changes between subgroups will be done by Kruskal-Wallis test and ANOVA test if assumptions of parametric tests will be met. Also adjusted analyses for age, sex and country effects will be done.
 
Time-to-event variables will be analyzed via a Cox proportional hazard regression model presenting hazard ratios and the corresponding 95% confidence intervals. Additionally, adjusted Cox models for age, sex and country effects will be presented. In addition, Kaplan-Meier curves will be presented for time-to-event variables. Two-sided 95%-CI will be presented for important parameters, but should be interpreted in an exploratory descriptive way.
 
All statistical testing (including hazard ratios, relative risks etc.) will be performed in an exploratory manner only. Details regarding statistical analyses will be described in the SAP and in the statistical section of the report.

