## 8 RESEARCH QUESTION AND OBJECTIVES OF THE OBSERVATION

### 8.1 Primary Objective

The primary objective is to document, in the real-world setting, the effectiveness of current treatment modalities in managing plasma levels of LDL-C in Very High Risk and High Risk (e.g. SMART score for Very High Risk patients and Framingham risk score for High Risk patients) patients requiring LMTs

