As the study is non-interventional, only data from the clinical routine treatment can be obtained. Therefore some information may be missing or unavailable. This needs to be taken into account when data are analyzed and reported.

No explicit non-eligibility criteria are defined to avoid selection of patients and thus violation of the 'real-life' principle.

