## 10.6 Assessments (according to the study type)

The investigators will be instructed about the correct documentation of the required variables for each patient in the eCRF. These data are available as part of the routine treatment. All examinations performed depend on the discretion and clinical routine of the physician. No diagnostic or monitoring procedures are applied to the patients in the study other than those performed as standard of care.

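### As section 9.7 stands, the 1-year LDL-C result is a complete-case estimate after two selection steps; the plan neither shows who is missing nor accounts for it

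*Combined protocol and SAP*

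**What the plan says.** Section 8.1 sets out to document "the effectiveness of current treatment modalities in managing plasma levels of LDL-C in Very High Risk and High Risk" patients who need lipid-modifying therapy. Section 9.7 adds: "No primary endpoint was defined in this study". In what follows, the 1-year LDL-C result therefore means the follow-up result that serves the primary objective.

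On whether a value will exist, section 9.4 states: "No visits or examinations, laboratory tests or procedures are mandated as part of this study". Table 1 repeats that "physicians will not be required to perform any mandatory laboratory assessment for this study", section 10.6 says "All examinations performed depend on the discretion and clinical routine of the physician", and section 9.3 lists the follow-up variables as recorded only when available.

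On who is analysed, section 9.7 says the Full Analysis Set (FAS) "consists of all patients from the BAS with available 1-year follow-up data", where BAS is the Baseline Analysis Set. The Summary (section 4) words the FAS slightly differently, as patients who completed the 1-year follow-up. Neither wording mentions LDL-C.

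On method, section 9.7 assigns 1-year changes in numerical parameters to a paired Wilcoxon test, or a paired t-test if its assumptions hold. Numerical summaries include the numbers of available and missing values. For categorical data, missing is named as a valid category at baseline only.

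Section 9.9 accepts that "some information may be missing or unavailable" and says this has to be considered in analysis and reporting, but names no method. Section 9.7 leaves detailed methodology to an SAP due by database lock; the text reviewed contains no such detail.

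**The concern.** A paired analysis uses only patients with both values. Here the second value depends on continued contact with the site and on a physician's decision to test. Either may be related to the LDL-C level itself, or to whether the patient is still on treatment. If so, the measured patients do not represent the enrolled ones, and a larger sample does not help: it narrows the interval around the wrong value.

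The plan takes care over representativeness at entry, with consecutive enrolment and a screening log, but has nothing comparable at follow-up. A reader of the report would see how many LDL-C values are missing, but not whose they are or how far the estimate could move. At stake is how well the 1-year figure describes real-world LDL-C control in the population the study set out to describe.

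**Working it through.** **The plan's own figures.** The plan gives no LDL-C availability rate, no dropout rate and no LDL-C precision, so there is no LDL-C figure to reproduce. Its only precision statement (section 9.5) concerns the relative risk of major vascular events: ±13% absolute and ±16% relative. The two agree with each other at a relative risk of 0.13/0.16 = 0.8125. They cannot be derived from 8000 patients without an event rate and a group split, and they make no stated allowance for missing data.

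**Selection steps, from sections 9.4, 9.7 and 10.6.**
1. BAS to FAS: patients with no 1-year follow-up data drop out, including those who leave care or die.
2. FAS to paired LDL-C: patients with follow-up data but no LDL-C at baseline or at 1 year drop out.

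**General size.** Let m be the share without a 1-year value. The complete-case mean minus the mean in all patients equals m × (mean in measured − mean in unmeasured). For m = 0.1 to 0.5 and a difference of 0.1 to 0.5 mmol/L (both assumed), the absolute bias runs from 0.1 × 0.1 = 0.01 to 0.5 × 0.5 = 0.25 mmol/L.

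**Precision for comparison.** The half-width is 1.96 × SD/√(8000 × (1 − m)), with an assumed SD of 1.0 mmol/L and ignoring clustering by site. It is 0.023 at m = 0.1 and 0.031 at m = 0.5. At m = 0.3 it is 0.026, so a difference of 0.026/0.3 = 0.09 mmol/L between measured and unmeasured patients already gives a bias equal to the half-width.

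**Illustration by discontinuation.** Inputs:
- share discontinuing, q: 30% and 50%, the ends of the 1-year statin range cited in section 7;
- gap between discontinuers and continuers at 1 year: 0.9 mmol/L, assumed equal to the LDL-C reduction in section 9.5, with equal baselines;
- testing rates t_d (discontinuers) and t_c (continuers): assumed.

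Share of discontinuers among the measured = q·t_d/(q·t_d + (1 − q)·t_c). Overstatement of the mean reduction = 0.9 × (q − that share).

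| q | t_d | t_c | Measured overall | Discontinuers among measured | Overstatement, mmol/L |
|---|---|---|---|---|---|
| 0.3 | 0.9 | 0.9 | 0.90 | 0.300 | 0 |
| 0.3 | 0.7 | 0.9 | 0.84 | 0.250 | 0.045 |
| 0.3 | 0.5 | 0.9 | 0.78 | 0.192 | 0.097 |
| 0.3 | 0.3 | 0.9 | 0.72 | 0.125 | 0.158 |
| 0.5 | 0.7 | 0.9 | 0.80 | 0.437 | 0.056 |
| 0.5 | 0.5 | 0.9 | 0.70 | 0.357 | 0.129 |
| 0.5 | 0.3 | 0.9 | 0.60 | 0.250 | 0.225 |

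The range 0.045 to 0.225 mmol/L is 5% to 25% of 0.9. At the matching sample sizes the half-widths are 1.96/√6720 = 0.024 and 1.96/√4800 = 0.028.

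**Opposite sign.** Suppose patients who stop or change therapy are retested more often, say t_d = 0.9 and t_c = 0.5. At q = 0.3 the discontinuer share among the measured is 0.27/(0.27 + 0.35) = 0.435, and 0.9 × (0.3 − 0.435) = −0.12 mmol/L. At q = 0.5 it is 0.45/0.70 = 0.643, giving −0.13. The complete-case result then understates the reduction.

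**The case against.** The strongest case for the plan is that this is a descriptive, non-interventional registry. Missing laboratory values come with that design, and not mandating tests is no error. Section 9.9 admits the gap, section 9.7 counts missing values for every numerical variable, and the Summary describes both BAS and FAS, so overall attrition would be visible. Section 9.7 covers only the main methods and leaves the rest to the SAP. It illustrates the paired tests with the risk score rather than LDL-C, and also says that no formal tests will be done. In previously treated patients, baseline LDL-C on current treatment also serves the primary objective and is untouched by follow-up selection.

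Much of this stands. The gap lies in the handling of missing data, not in its disclosure, and it concerns only the follow-up result. It does not remove the point. The paired method is stated for numerical parameters generally, and LDL-C is one. A descriptive estimate can be biased by selection as much as a tested one, and 95% intervals are planned. Counts show how many values are missing, not which patients lack them.

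A reader might go further and infer that effectiveness will be overstated because patients who stop therapy are the least likely to be tested. The documents do not say this. Section 7 links poor compliance to poor outcomes but not to testing, and the reverse pattern is also plausible. Nor should the point be put in terms of goal attainment, which appears in the background but not among the listed variables or planned analyses.

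**Conclusion.** The point holds for the 1-year LDL-C result that serves the primary objective. As written, that result is a complete-case estimate after two selection steps, and the stated analyses neither describe the unmeasured patients nor account for them, although section 9.9 calls for this to be considered.

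The possibility of selection follows from the documents; its direction and size do not. Under the stated testing assumptions the overstatement is 0.05 to 0.23 mmol/L. It is zero with equal testing rates and changes sign if the testing pattern is reversed. These figures rest on assumed testing rates, an assumed 0.9 mmol/L gap and statin discontinuation rates borrowed from the background section. What makes the point worth acting on is the contrast with precision: at about 8000 patients a modest bias exceeds a half-width of 0.02 to 0.03 mmol/L, so the interval would not warn the reader. This should be corrected in the analysis and reporting; it is no reason to change the design or add tests.

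**What to change.** In section 9.7, and in the SAP to which it defers:

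(a) Report the proportion of patients with a 1-year LDL-C value by treatment modality, risk stratum, country and baseline LDL-C. Compare patients with and without a value on baseline characteristics and, where documented, on treatment status at follow-up. This needs no modelling assumption.

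(b) Keep the paired complete-case result. Beside it, give an estimate for BAS patients alive at 1 year, by multiple imputation, a mixed model or inverse-probability weighting. Use baseline LDL-C, baseline covariates and the collected follow-up data on treatment change and discontinuation. A model with baseline covariates alone would not correct for missingness driven by stopping therapy after baseline. State how patients of unknown vital status are treated.

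(c) Add a shift (delta) analysis in which the values assigned to unmeasured patients are moved up and down by stated amounts. This matters most for patients outside the FAS, whose treatment data after baseline may be absent.

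Use one FAS wording in the Summary and in section 9.7.

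The cost is SAP wording and modest extra analysis. No tests, visits or data items are added. The estimate in (b) relies on a missing-at-random assumption, which should be stated; (c) shows how much depends on it.
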